### **NON-TECHNICAL SUMMARY**

Provide a non-technical summary of the proposed research project that can be understood by IRB members with varied research backgrounds, including non-scientists and community members. The summary should include a brief statement of the **purpose of the research** and **related theory/data supporting** the intent of the study as well as a brief description of the **procedure(s) involving human subjects**. *This summary should not exceed ½ page.*

The goal of this research is to determine whether 10-weeks of exercise training can benefit asthmatic children and young adults with a history of exercise-induced bronchoconstriction (EIB). Physical activity is a double-edged sword for children and adults with asthma. On the one hand, exercise is a common trigger of wheezing (EIA—exercise induced asthma), occurring in as many as 80% of affected individuals. On the other hand, exercise and fitness training seem to benefit asthma control. The underlying causes responsible for EIA remain unknown. We will, for the first time, test hypotheses focused on mechanisms of exercise training, asthma and Exercise Induced Bronchoconstriction that involve the genomic changes of circulating white blood cells. We will also study an exciting newly discovered aspect of gene expression regulation in the white blood cells known as epigenetics: a process that takes place when genomic changes happen as a result of exposure to the environment. Our study is based on emerging exciting new data from this and other laboratories demonstrating that (1) white blood cells play an important role in bronchoconstriction[1,2] in children, (2) gene and cytokine expression in circulating white blood cells are abnormal in asthma,[3,4] and (3) brief exercise may change genomic and inflammatory-profiles of these cells.[5-7] Each participant will undergo a training regimen. The participants will come to our lab up to three times before the beginning of the training program, and up to three times immediately at the end of the exercise program to perform Exercise Fitness Session and Exercise Challenge Sessions. The visits may occur in any order, depending on the availability of the laboratory and timing. In the Exercise Fitness Session, the participant will perform a standard exercise test to determine fitness and will perform a series of pulmonary function tests. In addition, the participants will have two DXA scans to determine body composition (prior to

beginning the training sessions and after the training sessions have been completed). In one of the Exercise Challenge Sessions, the participants will have an indwelling venous catheter placed in an arm vein so that we can draw blood samples. In another Exercise Challenge Session we will perform non-invasive blood flow measurement. The participants will exercise using a protocol we have performed in our lab on hundreds of young adults and children in which the subject uses a stationary bicycle and completes a series of 10, 2-minute bouts of exercise interspersed with one-minute rest periods. The exercise-training intervention is built on effective social cognitive and self-determination approaches to health-behavior change. Physical activity is an essential component of growth and health in children, thus, this research will lead to improved clinical uses of exercise as preventive and adjunctive therapy in the current epidemic of childhood asthma.

## **SECTION 1: PURPOSE AND BACKGROUND OF THE RESEARCH**

1. Describe the **purpose of the research** project and state the overall objectives, specific aims, hypotheses (or research question) and scientific or scholarly rationale for performing the study.
2. Provide the **relevant background information** on the aims/hypotheses (or research question) to be tested and the procedures/products/techniques under investigation.
3. Include a description of the **predictor and outcome variables**, as appropriate.
4. Include a critical evaluation of **existing knowledge**, and specifically identify the information gaps that the project intends to address.
5. Describe **previous research** with animals and/or humans that provides a basis for the proposed research. **Include references/citations**, as applicable.

*This section should not exceed 4 pages.*

The goal of this research is to determine whether an exercise training intervention can benefit asthmatic children and adults with a history of exercise-induced bronchoconstriction (EIB). We will, for the first time, test hypotheses focused on mechanisms of asthma and EIB that involve genomic and epigenetic regulation of circulating leucocytes. In addition, we will gauge the effect of training on airway inflammation, asthma control, and muscle and cardiorespiratory fitness. Increasingly, asthma is viewed as a condition not just of the lungs but involving a broad range of impaired inflammatory response mechanisms at a systemic level. Our study is based on emerging exciting new data from this and other laboratories demonstrating that (1) first-responding innate immune cells (such as, neutrophils and monocytes) play key roles in bronchoconstriction in children, (2) gene and cytokine expression in circulating neutrophils is abnormal in asthma and (3) brief exercise alters genomic (including epigenetic) and inflammatory-functional profiles of these cells. Collectively, these new insights lead to the premise that exercise training may benefit such children specifically by conditioning inflammatory control mechanisms in the leucocytes. Physical activity is an essential component of growth and health in children, thus, this research will lead to improved clinical uses of exercise as preventive and adjunctive therapy in the epidemic of childhood asthma.

**Specific Aims:** Using a novel exercise training treatment intervention designed specifically to promote sustainability and generalizability in children and adults with chronic diseases like asthma, we plan to:

*Primary Aims:*

1. Elucidate key abnormal genomic (including epigenetic) responses to brief exercise in leucocytes of children and adults with persistent asthma
2. Identify the effect of exercise training on the key genomic exercise response mechanisms in leucocytes in children and adults with persistent asthma

*Secondary Aim:*

3. Assess the clinical impact of exercise training in children and adults with persistent asthma on: (a) exercise induced airway inflammation, (b) asthma control, and (c) cardiorespiratory fitness and muscle adaptation.

**Hypotheses:**

1. Leucocytes genomic, epigenetic, and functional regulation is abnormal in asthmatic individuals leading to a greater pro-inflammatory profile in response to a brief exercise challenge.
2. The exercise-training treatment will attenuate pro-inflammatory and intensify anti-inflammatory activity of leukocytes in response to brief exercise challenge.
3. The exercise-training treatment will diminish exercise-induced bronchoconstriction and its accompanying airway inflammation and improve asthma control.

**Impact:** Despite much recent progress in understanding asthma pathophysiology and the development of new therapies, the health care use associated with asthma, and the disruptions it causes to family and community life, have not decreased substantially. The link between physical activity and asthma is strong, but remains enigmatic. Physical activity is a “double-edged sword” for the people with asthma. On the one hand, exercise is a common trigger of wheezing in asthma, occurring, in some studies, in as many as 80% of affected children. On the other hand, exercise and fitness training seem to benefit asthma control in many affected children.

As succinctly stated by Lucas and Platts-Mills, *“It is our belief that an exercise prescription should be part of the treatment for all cases of asthma. The real question is whether prolonged physical activity and, in particular, outdoor play of children plays a role in prophylaxis against persistent wheezing. If so, the decrease in physical activity might have played a major role in recent increases in asthma prevalence and severity.”* As recently noted by Voelkel and Spiegel, *“In spite of numerous attempts to control asthma by treatment with bronchodilators, steroids, antigen-directed desensitization, and IgE-directed therapy, use of leukotriene receptor blockers and mast cell release inhibitors, a true control of the asthma syndrome with its multiple manifestations (exercise-induced, nocturnal, steroid-resistant, etc.), has so far eluded us. The reason is that...the disease... is perhaps much more an integrated system problem than only a bronchial problem.”* The progress we have made in the past years supports the notion that EIB involves abnormalities in systemic, circulating leucocytes, particularly in response to exercise. Understanding these mechanisms will lead to improved use of exercise as adjunctive and preventive therapy in pediatric asthma.

Stevens and coworkers recently published an eloquent and succinct assessment of the scale of the public health problem associated with childhood asthma, *“As many as 6.5 million children in the United States (or 8.9% of all children 0–18 years) have been diagnosed with asthma and are reported to currently have the disease.”* *The burden of asthma in childhood is tremendous, accounting for about 754,000 emergency department visits and 198,000 hospitalizations each year, and costing more than \$850 million annually.* *This burden is greater for vulnerable children, where rates of emergency visits and hospitalizations are double or triple among the poor, racial/ethnic minorities, and the uninsured.* Clark and coworkers recently noted in a review of the effectiveness of educational and behavioral asthma interventions, *“The paradox of asthma is that, although our understanding of its pathophysiological features and the therapies available for treating the disease have increased significantly over the past 2 decades, the prevalence of asthma, the health care use associated with it, and the disruptions it causes to family and community life have not decreased substantially. These facts suggest a need for interventions that enable individuals, families, communities, and health care providers to manage asthma and its consequences effectively.”*

**Critical exercise-asthma treatment issues remain enigmatic and poorly studied**, ranging from rare but tragic instances of death due to EIB in asthmatic youth to the lack of clinically validated paradigms of “return to play” following an exercise-associated asthma attack. Despite the accepted clinical goal of ensuring that children with asthma fully participate in all

types of exercise, physical fitness and participation in physical activity have repeatedly been shown to be impaired in children with asthma. Participation in school PE among children with asthma is reduced by as much as 40%. Moreover, Conn and coworkers recently discovered excessive use of electronic media in children with asthma, particularly in those with activity limitation. Whether these findings result from the *perception* of disability, or from poorly managed exercise-associated wheezing, is not known. But whatever the causes, **reduced participation in physical activity is an ominous finding in a child with asthma.**

There is emerging data suggesting that exercise is beneficial for asthma in terms of disease control and pathogenesis. A growing number of animal studies (such as those by Pastva *et al.* and Hewitt *et al.*) examined how brief exercise and exercise training modulated subsequent lung inflammatory responses to ovalbumin (OVA) challenge in OVA-sensitized rats. These studies demonstrated a generally moderating effect of exercise on subsequent lung inflammatory responses to acute allergen challenges specifically by decreasing NF- $\kappa$ B nuclear translocation and I $\kappa$ B $\alpha$  phosphorylation thereby diminishing key pro-inflammatory (and possible neuroadrenergic) control pathways. In children, studies of the benefits of exercise and physical activity have yielded mixed results (perhaps due to a number of the barriers to such research outlined below), but a recent study from Bonsignore *et al.* concluded that exercise training in combination with anti-inflammatory therapy might synergize to attenuate airway response to methacholine challenge in asthmatic children.

It is increasingly recognized that poorly controlled asthma in children can set the stage for lung disease in adulthood, thus, efforts to improve fitness and asthma control in children and adolescents, a “critical period” of growth and development, are bound to have effects on health that last a lifetime.

### **SECTION 3: RESEARCH METHODOLOGY/STUDY PROCEDURES**

#### **A. Study Design and Procedures**

1. Provide a **detailed chronological description of all study activities** (e.g., pilot testing, screening, intervention/interaction/data collection, and follow-up) and **procedures**.

Include an explanation of the study design (e.g., randomization, placebo-controlled, cross-sectional, longitudinal, etc.)

- a. Indicate how much **time will be required of the subjects**, per visit and in total for the study.
- b. Indicate the **setting where each procedure will take place**/be administered (e.g. via telephone, clinic setting, classroom, via email). *Note: If any of the procedures will take place at off-campus locations (e.g., educational institutions, businesses, organizations, etc) Letters of Permission are required.*
- c. If a procedure will be completed more than once (e.g., multiple visits, pre and post survey), indicate **how many times** and the **time span** between administrations.

2. **For studies that involve routine (standard of care) medical procedures:**

Make clear whether procedures are being done for clinical reasons or for study purposes, including whether the procedures are being done more often because of the study. Use the following guidelines to determine the extent to which standard procedures and their associated risks need to be described in protocol:

- a. If the standard procedure is not explicitly required by the study protocol, the protocol need not describe that procedure or its risks.
- b. If the standard procedure is a main focus of the study (e.g., one or more arms of a randomized study is standard) or is explicitly required by the study protocol, the protocol must include a full description of the procedure and its risks.]

3. It is **strongly recommended** that you include a table of visits, tests and procedures. Tables are easier to understand and may help to shorten long repeated paragraphs throughout the narrative.

4. If study procedures include collecting **photographs, or audio/video recording**, specify whether any subject identifiable information will be collected and describe which identifiers will be collected, if any.

5. Describe how the **subject's privacy will be protected** during the research procedures.

*Note: This is not the same as confidentiality (see the [Privacy and Confidentiality web page](#)).*

6. Be sure to submit **data collection instruments** for review with your e-IRB Application (e.g., measures, questionnaires, interview questions, observational tool, etc.).

A summary of the research activities can be found in Table 1 at the end of this section.

This is a training program that can last up to 12 weeks and includes:

1. Testing the participants in the UCI Pediatric Exercise Research Center (PERC) (at the beginning and again at the end of the training program).
2. Ongoing training will continue outside of UCI with professional personal trainers
3. Collecting saliva to measure stress and inflammatory mediators (prior to the beginning, in the middle and again at the end of the training program).
4. Monitor exercise intensity levels in the field, during an exercise session and physical activity levels over full 7 days (weeks 1, middle of the training program and the last week of the training program).
5. Executive Function assessment (at the beginning and again at the end of the training program).
6. Dietary log book (at the beginning and again at the end of the training program).

Before and at the end of the training intervention the subjects will arrive to the Pediatric Exercise Research Center, for up to 3 sessions every time, to perform the following assessments:

**Baseline assessments**

1) Fitness Assessment Session. Participants will undergo a comprehensive clinical history and physical examination with determination of Tanner stage, vitals and anthropometric

measurements including DXA-determined body composition and bone density. Aerobic fitness will be assessed using incremental cycle-ergometer exercise test to determine peak VO2.

2) Exercise Challenge Session + blood draws.

3) Exercise Challenge Session + blood flow measurements.

The same sessions will be repeated for each subject once the training regimen is complete, and may be held in any order.

The Fitness Assessment Session and the Exercise Challenge Session will take place no less than 48 hours apart and no more than four weeks apart.

A portion of these visits may take place at the Beckman Laser Institute (BLI). The BLI is located next to the PERC/ICTS Exercise Lab. The BLI is providing numerous pieces of equipment that will be used for blood flow measurements.

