- Exercise testing will be performed at the UCI PERC/ICTS Applied Physiology/Human Performance Core Laboratory. To measure cardiorespiratory responses to exercise and assess fitness, we will use a ramp-type progressive exercise test on an electronically braked cycle ergometer (SensorMedics Ergoline 800S, Yorba Linda, CA) (1), through a method previously designed for children and adolescents (2). The work rate will increase by 10 W per min (or adjusted according to the subject's age and fitness level) so that the total exercise time will roughly equal 8-12 min, and each subject will exercise to the limit of his or her tolerance. During the exercise, the participant will breath through a mouthpiece, a noseclip will be worn, and measurements of their breath will be taken. Gas

exchange will be measured breath-by-breath using a metabolic cart (SensorMedics VMax 229, Yorba Linda, CA). The metabolic cart measures inhaled as well as exhaled carbon dioxide and oxygen by use of a mouthpiece and noseclip allowing gas exchange measures in the breath. After exercise, participant's heart rate will be monitored until it reached pre-exercise values. If any faintness or dizziness is reported, participants are asked to lay down and are then allowed to leave after 30-min of cessation of symptoms. Gas exchange will be measured breath-by-breath (3). Multiple Pulmonary Function Tests (PFT's) will be performed prior to and following the exercise challenge. This approach has been used extensively in our laboratory in children, adolescents and adults.

- Diet: During the week of physical activity evaluation, participants will complete a three-day food record, to be analyzed by the UCI PERC bionutrition using the Nutrition Data System for Research (University of Minnesota, Minneapolis, MN), a specialized software containing a nutrient profile of over 18,000 foods.

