### ***Exercise Challenge Session and Blood Draws--before and after the training program***

*The trainers are aware that they are responsible for the children's safety. All parents will be strongly encouraged to attend the training session with their child. The trainer is aware of abuse reporting procedures.*

- The exercise session will occur no less than 48 hours and no later than 4 weeks apart from the **Fitness Assessment Session**. Participants will arrive in the morning after an 8 hour fasting. Participants will be able to continue to use their long-term asthma control medications during the period in which they are required to fast. An indwelling catheter will be placed in an antecubital vein of each subject by trained physicians and/or nurses with specific experience in pediatric procedures of this nature. If requested, a cream will be used to numb the site for the catheter placement to reduce discomfort. The indwelling catheter will allow multiple blood draws without the possible adrenergic stimulation associated with multiple needle sticks.
- After a 20 min rest, PFTs and baseline blood draw will be acquired and exercise can begin. Exercise will consist of a series of 10, 2-min bouts of constant work rate cycle ergometry with 1-min resting intervals between each exercise bout. The work rate will be individualized for each subject, and equivalent to the work rate corresponding to 50% of the difference between the anaerobic or lactate threshold (LT--determined non-invasively from the ramp test) and peak VO2. We use this approach to ensure that the exercise input is standardized to physiological indicators of each individual subject's exercise capability.
- During exercise and for the 60 min following exercise additional blood samples will be acquired. The total amount of blood withdrawn at each timepoint will be up to 80 ml, or ~ 5 tablespoons for children and up to 160 ml for adults (no more than 5ml/Kg), amounts we routinely collect in children and adults without causing discomfort. If any faintness or dizziness is reported, participants are asked to lay down and are then allowed to leave after 30-min of cessation of symptoms. Collected blood samples will be analyzed for glucoregulatory hormones, pro-/anti-inflammatory cytokines, growth factors, markers of oxidative stress, gene and microRNA expression studies and leukocytes functional assays.

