In the Field (Approximately 1 hour per session for up to 30 sessions)	Exercise-Training	
 
• Personal trainers, small-groups, community venues, tailored training sessions x 3 weekly
 

	Compliance	
 
Attendance at exercise sessions
 
Exercise intensity will be assessed using heart rate (HR) monitors
 

Week 6-7		
At Home	Actigraph	
 
Assessment of physical activity over 7 days
 

At Home	Saliva Collection	
 
3 times a day (3 samples) over two consecutive days
 

Week 11		
At Home	Actigraph	Assessment of physical activity over 7 days
At Home	Saliva Collection	3 times a day (3 samples) over two consecutive days
Weeks 12		
PERC/ICTS Lab: Fitness Assessment (Approximately 2 hours)	Clinical Assessment	
 
Clinical Evaluation
 
Vitals and anthropometric measures (blood pressure, temperature, height and weight)
 

	Progressive Exercise Testing	
 
Ramp type protocol to assess peak VO2 (aerobic fitness)
 
Pre- and post-exercise Exhaled NO measurements
 
Pre- and post-exercise PFTs
 
Pre- and post-exercise blood flow measurements
 
Pre- and post-exercise saliva collection
 

	DXA	
 
Body composition (lean and fat mass)
 

	Executive Function Test	
 
Executive function tasks – 5 min of specific computer games
 

PERC/ICTS Lab: Exercise Challenge (separate at least 48 hours from the Fitness Assessment visit) (Approximately 3 hours)	Exercise Challenge on a cycle ergometer (10 x 2-min bouts @ ~70% peak work rate, with 1-min intervals)	
 
Blood draw* (before, immediately after, and one-hour after the exercise challenge).
 
Pre- and post-exercise Exhaled NO measurements
 
Pre- and post-exercise PFTs
 
Pre- and post-exercise saliva collection
 

PERC/ICTS Lab: Exercise Challenge (Approximately 2 hours)	Exercise Challenge on a cycle ergometer (10 x 2-min bouts @ ~70% peak work rate, with 1-min intervals)	
 
Pre- and post-exercise blood flow measurements
 
Pre- and post-exercise PFTs
 

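### The sessions may be held in any order and no ramp test is named for the post-training challenge load, so relative load can depend on booking

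*Protocol*

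**What the plan says.** Section 3A of the protocol (Exercise Challenge Session and Blood Draws) covers the challenge before and after training. It places the work rate halfway between the lactate threshold and peak VO2, with the threshold "determined non-invasively from the ramp test". The reason given is: "We use this approach to ensure that the exercise input is standardized to physiological indicators of each individual" participant. Table 1 describes the challenge in Weeks 1 and 12 as "10 x 2-min bouts @ ~70% peak work rate, with 1-min intervals", which also needs a ramp result.

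The ramp belongs to the Fitness Assessment Session, held once before and once after training, in which "each subject will exercise to the limit of his or her tolerance".

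Two places deal with session order. Section 3A, Baseline assessments, says of the post-training visits: "The same sessions will be repeated for each subject once the training regimen is complete, and may be held in any order". The Non-Technical Summary, having described the visits before and after training, says: "The visits may occur in any order, depending on the availability of the laboratory and timing".

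The spacing rule in the challenge section reads "The exercise session will occur no less than 48 hours and no later than 4 weeks apart from the" Fitness Assessment Session. Baseline assessments gives the same window, and Table 1 repeats the 48-hour separation. None of these places the ramp first, and no section says which ramp sets the post-training work rate.

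**The concern.** The challenge is the stimulus under which the main outcomes are measured. Its blood draws give the primary outcome, leukocyte gene expression (Table 1 footnote; Section 3B). Exhaled NO and lung function are also measured around it. If the stimulus shifts between Week 1 and Week 12 for reasons of scheduling, part of the before-after change reflects the load and not the training.

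- **Aim 2 (two-sample comparison of change).** Both groups train, so a shift common to both largely cancels. Mixed ramp sources add variance. They bias the comparison only if scheduling or fitness gain differs between groups.
- **Aim 3 (paired before-after tests).** There is no group contrast to cancel a shift, so a changed relative load can enter the difference in challenge exhaled NO and lung function directly. Section 4A names exhaled NO after the challenge as a secondary outcome, listing it there under Aim 2. An old-ramp challenge after a fitness gain is lighter than intended. If the airway response falls with load, which is an assumption, the difference moves the way Hypothesis 3 predicts.
- **Not affected by post-training order.** Exhaled NO and lung function around the ramp itself, where effort is to tolerance; the fitness, muscle and asthma-control outcomes; and Aim 1.

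The Non-Technical Summary extends the permission to the pre-training visits, where a challenge held first would have no study ramp from which to set its load.

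**Working it through.** The protocol has no figure of its own to reproduce here. The check sets its statements together and then illustrates the size.

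**Step 1. What each permitted order allows after training.**

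| Order in Week 12 | Ramp available at the challenge | Age of that ramp |
|---|---|---|
| Fitness Session first | Week 12 ramp (or Week 1) | 48 hours to 4 weeks for the Week 12 ramp |
| Challenge first | Week 1 ramp only | 12 − 1 = 11 weeks |

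Both rows satisfy the spacing rule, since a Fitness Session held after the challenge can still fall 48 hours to 4 weeks from it. The rule asks for separation and gives no direction.

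**Step 2. Relative load when the Week 1 ramp is kept, on Table 1's scale.** Inputs: intended load L = 70% of peak work rate (Table 1, approximate); gain g in peak work rate, which the protocol does not give and which is assumed at 5%, 10% or 15%. Load as a share of the new peak is L/(1+g). The shortfall against target is 1 − 1/(1+g).

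| Assumed g | 70/(1+g) | Points below 70 | Relative shortfall |
|---|---|---|---|
| 5% | 66.7% | 3.3 | 4.8% |
| 10% | 63.6% | 6.4 | 9.1% |
| 15% | 60.9% | 9.1 | 13.0% |

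For a participant tested on the new ramp the shortfall is zero.

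**Step 3. The same on the threshold-to-peak scale of Section 3A.** Let the threshold be a fraction f of peak (assumed), both on the work-rate scale, with the Week 1 peak set to 1. The Week 1 work rate is W = (1+f)/2. If threshold and peak both rise by g, the position of W between them becomes (W − f(1+g)) / ((1+g)(1 − f)), against the intended 50%.

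| Assumed g | f = 0.5, W = 0.75 | f = 0.4, W = 0.70 |
|---|---|---|
| 5% | 0.225/0.525 = 43% | 0.28/0.63 = 44% |
| 10% | 0.20/0.55 = 36% | 0.26/0.66 = 39% |
| 15% | 0.175/0.575 = 30% | 0.24/0.69 = 35% |

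The two descriptions of the load agree only if f is about 0.4, because (1 + 0.4)/2 = 0.70; f = 0.5 gives 0.75. The two passages need reconciling in any case. This check does not say which is right.

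**Step 4. From one participant to the study.** If a share p is tested challenge-first on the Week 1 ramp and the rest on the new ramp, and all have the same gain, the mean shift in load is p times the shift in Step 2. The added between-participant variance in load is p(1 − p) times its square. Turning this into a bias in exhaled NO, lung function or gene expression needs p and a load-response slope, and the protocol gives neither.

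**The case against.** The strongest reply is that the protocol can be read as already tying each challenge to the ramp of its own phase. The challenge section applies to both phases, pairs the challenge with the Fitness Session within four weeks, and states that the load should match the individual's capability. An 11-week-old ramp fits neither the pairing nor the purpose. Table 1 lists the Fitness Session first in both phases. At baseline, the VO2max limit and the fitness criteria in Section 4 make an early ramp likely. This is probably what the sponsor intends, but it does not withdraw two explicit permissions to use any order. A requirement that sessions be a certain time apart does not say which comes first.

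The reply also notes that load depends on booking only if staff change the ramp source with visit order. That is correct. If every post-training challenge used the Week 1 ramp, order would not matter, although every participant who gained fitness would then be challenged at a lower relative load. If every one used the new ramp, challenge-first could not occur. The protocol fixes neither rule, so the mixture is open.

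Finally, the size rests wholly on assumed gains, a 5% gain moves an approximate 70% only slightly, and exhaled NO and lung function around the ramp give evidence on Hypothesis 3 that does not depend on the challenge load. These points stand. They limit the weight of the concern and do not remove it.

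**Conclusion.** The concern holds. The permission to hold sessions in any order conflicts with the protocol's own rule that the challenge load be standardised to the participant's capability, and the ramp that governs the post-training load is not named.

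The textual conflict is certain; its effect on the results is not. With assumed gains of 5% to 15%, a participant tested challenge-first on the Week 1 ramp would work at a load 4.8% to 13.0% lighter than the stated target. For Aim 2 the expected consequence is extra variance, with bias only if scheduling or gain differs by group. For Aim 3 the exposed results are the paired changes in exhaled NO and lung function around the challenge. The direction favourable to Hypothesis 3 depends on the assumption that the airway response falls with load. The change should be made, with medium confidence that it matters for the results.

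**What to change.** 1. In the Non-Technical Summary and in Section 3A, Baseline assessments, replace the any-order permission with a statement that the Fitness Assessment Session precedes the challenge sessions in each phase. The two challenge sessions may stay in either order.
2. In the challenge section, name one ramp source for the post-training work rate that applies to every participant. The choice is the sponsor's, and it decides whether relative or absolute load is held constant across training, so it should be explicit and consistent with the stated purpose of standardisation. If the Week 1 ramp were chosen, the order rule would no longer be needed for the post-training load, but it would still be needed at baseline.
3. Record the work rate used and its ramp source at every challenge, so that any departure can be seen and examined in the analysis.

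The cost is protocol wording, two recorded items per challenge and slightly less flexible laboratory booking. No visit or test is added, and no sample size or power figure changes.
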